#### **4.1.4 History of Alopecia**

The type of Alopecia (AT or AU) and prior therapies for alopecia will be summarized by frequency distributions. The time since onset of the current episode of alopecia at entry will be summarized using descriptive statistics (n, mean, standard deviation, median, minimum, and maximum). Summaries will be generated for the AS population. Histological/Cytologic information will be tabulated.

#### **4.1.5 Prior and Concomitant Medications, Therapies and Procedures**

Medications are coded using the WHO Drug Reference. Prior and concomitant medications are listed only. The period(s) in which the medications were administered are flagged.

#### **4.1.6 Exposure to Study Medication and Study Medication Administration**

Exposure will be summarized and listed for the AS population with separate summaries from double-blind and open-label periods. Additionally, the combined exposure to ATI-50002 from the double-blind and open-label periods will be tabulated.

The duration of treatment, total weight, total volume, and average volume per application will be summarized using descriptive statistics (n, mean, SD, median, minimum and maximum).

#### **4.1.7 Major Protocol Violations**

Protocol violations will be identified to measure adherence to key aspects the protocol. Prior to unblinding the sponsor will assess the data and identify all major and minor protocol deviations. Specific data fields that will be examined to identify protocol deviations include entrance inclusion/exclusion criteria and prohibited prior and concomitant medications as well as all deviations identified by the investigator. All protocol violations will be listed, and major protocol violations will be summarized (n and percent) by randomized treatment group for all violations during the double-blind period.

## **4.2 Pharmacokinetic Endpoints**

### **4.2.1 Blood Levels of ATI-50002**

The blood levels of ATI-5002 will be listed only.

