Blood samples for analysis of the concentration of ATI-50002 will be taken from the first 6 subjects enrolled into the study at Day 1 (Visit 2) and Day 28 (Visit 6) at predose (0 hr), 1, 2, 4, 8 and on Day 2 (Visit 3) and Day 29 (Visit 7) at 24 hours post dose. For each subject, standard PK parameters will be calculated, based on the plasma concentrations of ATI-50002.

Scalp Biopsy

The concentration of ATI-50002 will be determined in a 4-mm punch biopsy of the scalp taken 24 hours post study medication application in the office on Day 2 (Visit 3) and Day 29 (Visit 7).

Pharmacodynamic (Biomarker) Analyses**ALADIN Scores**

The cytotoxic T lymphocyte infiltration (CTL), Interferon (IFN-gamma), and hair keratin (KRT) ALADIN scores will be calculated for each scalp biopsy sample as previously described in Xing et al, 2014, Jabbari 2016. Change in ALADIN scores within individual subjects will be assessed between Baseline (Visit 2), Day 29 (Visit 7) and Week 28 (Visit 13) for subjects enrolled into the open-label extension.

Histology

Scalp punch-biopsies will be formalin-fixed and paraffin-embedded and will be sectioned both vertically and horizontally by a qualified dermatopathologist. Specimens will be stained with hematoxylin and eosin (H&E) for routine histopathologic evaluation that will include (but is not limited to) diagnosis and evaluation of the presence, quantity, location, and quality of any hair, hair follicles, and inflammatory infiltrate present. Additionally, immunohistochemical (IHC) stains will be employed to identify immune cell populations (e.g., Lymphocytes, cytotoxic T-lymphocytes [CTLs]), and hair-specific keratins. IHC stains to assess inflammatory responses will include (but not be limited to) CD8, HLA-DR and ICAM-1. Data will be presented as percent change from baseline in the number of cells/ high power field in regions of interest (peribulbar areas) and in percent change from baseline in the number of cells/mm².

Blood for Immunology

Blood samples will be stained with cell surface antibodies for fluorescence acquisition cell sorting (FACS) analysis. FACS experiments will allow for assessment of the subset and activation status of immune cells involved in AA.

Safety Data

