7. INVESTIGATIONAL PLAN

7.1. Overall Study Design

In the double-blind period, this Phase 2, multicenter, randomized study is designed to evaluate the safety, tolerability, pharmacokinetics and pharmacodynamics of ATI-50002 Topical Solution in subjects with AU and AT. Subjects will be required to have a clinical diagnosis of stable, clinically typical AU or AT for a duration of at least six months up to and including seven years. A total of 12 subjects will be randomized.

During the screening period, subjects will be assessed for eligibility into the study. Subjects who meet all the entry criteria will be randomized 2:1 to ATI-50002 Topical Solution, 0.46% or Vehicle Topical Solution and will apply a minimum of 1.5 mLs up to a maximum of 4 mLs of study medication to the entire scalp twice-a-day for 28 days. On Day 1 (Visit 2), Day 28 (Visit 6), and Day 196 (1 day prior to Visit 13), subjects will apply study medication once-a-day.

Blood samples for concentrations of ATI-50002 will be collected from the first 6 subjects enrolled into the study on Day 1 (Visit 2), and Day 28 (Visit 6) at pre-dose and 1, 2, 4, 8 hours post dose and on Day 2 (Visit 3) and Day 29 (Visit 7), 24 hours post-dose. Blood samples for immunology will be collected on Day 1 (Visit 2) before study medication application, and on Day 29 (Visit 7), 24 hours after study medication application on Day 28 (Visit 6). A 4-mm punch biopsy of the scalp will be obtained to determine the concentration of ATI-50002 in the scalp skin on Day 2 (Visit 3) 24 hours after study medication application on Day 1 (Visit 2) and on Day 29 (Visit 7), 24 hours after study medication application on Day 28 (Visit 6). A 4-mm punch biopsy will be obtained to determine histology and immunology prior to study medication application on Day 1 (Visit 2). Additional 4-mm punch biopsies to determine histology and immunology will be collected on Day 29 (Visit 7) and Day 197 (Visit 13), 24 hours after study medication application on Day 28 (Visit 6) and Day 196. Safety and tolerability will be evaluated at each study visit by assessment of adverse events and vital signs, and at select visits, ECGs and clinical laboratory tests will be completed.

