⁹ Subjects must be instructed to apply the study medication according to the instructions in Appendix 1. Subjects will apply the first dose of study medication on the morning of Day 1 (Visit 2) and the last application of study medication on the morning of Day 28 (Visit 6), under the instruction and supervision of the study staff. Study medication at these visits should be applied in the morning to allow the 8-hour post dose assessments to occur at a reasonable time. On Day 1 (Visit 2) and Day 29 (Visit 7) subjects will only apply study medication once-a-day in the office.											
¹⁰ PK: A 4mm punch biopsy must be obtained on Day 2 (Visit 3) and Day 29 (Visit 7) 24 hours (± 30 minutes) after study medication application on Day 1 (Visit 2) and Day 28 (Visit 6).											
¹¹ PD: A 4mm punch biopsy must be obtained on Day 1 (Visit 2) before application of first dose of study medication and Day 29 (Visit 7) 24 hours (± 30 minutes) after study medication application. Subjects that choose to continue in to open-label extension treatment will also have a 4mm punch biopsy collected on Day 197 (Visit 13).											
¹² PK: The first 6 subjects enrolled in the study will have the blood PK testing performed. Blood for PK sampling will be obtained on Day 1 (Visit 2) and Day 28 (Visit 6), just prior to study medication application (predose), and 1, 2, 4, 8 hours post dose and on Day 2 (Visit 3) and Day 29 (Visit 7), 24 hours after study medication application (on Day 1 (Visit 2) and Day 28 (Visit 6). See Section 9.3.2 for PK sample draw time windows.											

	Open-Label Treatment										Post-Treatment ¹⁷
	Visit 8	Visit 9	Visit 10	Visit 11	Visit 12	Call	Visit 13	Optional Visit (Suture Removal)	Visit 14	Visit 15	
Week	8	12	16	20	24	28	28	30	40	52	56
Treatment Day ¹⁷	57 (OLE 28)	85 (OLE 56)	113 (OLE 84)	141 (OLE 112)	169 (OLE 140)	196 (OLE 167)	197 (OLE 168)	211 (OLE 182)	281 (OLE 252)	365 (OLE 336)	59/393 (OLE 364)
Treatment Window(days)	± 3	± 3	± 3	± 3	± 3	± 3	± 3	± 3	± 7	+7	± 3/± 7
¹³ Blood for immunology will be obtained prior to administration of study medication on Day 1 (Visit 2) and on Day 29 (Visit 7) 24 hours (± 30 min) after study medication application on Day 28 (Visit 6). Subjects that choose to continue in to open-label extension treatment will also have blood for immunology collected on Day 197 (Visit 13).											

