9.3.2. Blood Samples (Double-blind Period)

For the first six subjects enrolled into the study, blood samples for PK analysis of ATI-50002 will be collected by a qualified staff member. On Baseline/ Day 1 (Visit 2) and Day 28 (Visit 6) blood samples will be collected at predose (0-hour) (just prior to study medication application in the morning) and then at the following times **after study medication application**:

- 1 hour (\pm 5 minutes)
- 2 hours (\pm 10 minutes)
- 4 hours (\pm 10 minutes)
- 8 hours (\pm 10 minutes)

On Day 2 (Visit 3) and Day 29 (Visit 7)

- 24 hours (\pm 30 minutes)

The bioanalytical laboratory will provide instructions on the collection and shipment of samples.

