12.4. Pharmacokinetic Analyses

Blood Samples

Blood samples for analysis of the concentration of ATI-50002 will be taken from the first 6 subjects enrolled into the study on Baseline/Day 1 (Visit 2) and Day 29 (Visit 7) at predose (0 hr), and 1, 2, 4, 8 hours after study medication application and on Day 2 (Visit 3) and Day 29 (Visit 7), 24 hours post dose. For each subject, standard PK parameters (C_{max} , T_{max} , AUC_{0-t} , $AUC_{0-\infty}$, $t_{1/2}$) will be calculated, as a minimum and whenever possible, based on the plasma concentrations of ATI-50002.

Scalp Biopsy

The concentration of ATI-50002 in skin will be determined in a 4-mm punch biopsy of the scalp taken on Day 2 (Visit 3) and Day 29 (Visit 7) 24 hours post study medication application in the office on Day 1(Visit 2) and Day 28 (Visit 6).

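### The SAP lists plasma ATI-50002 levels only, without the per-subject PK parameters planned in protocol 12.4, and SAP 4.8 neither declares nor explains the change

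*SAP*

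**What the plan says.** Both documents place pharmacokinetics in the primary objective (Protocol 5.1.1; SAP 1.1). Protocol 12.4 names five plasma parameters (Cmax, Tmax, AUC0-t, AUC0-∞ and half-life), which for each subject "will be calculated, as a minimum and whenever possible, based on the plasma concentrations of ATI-50002". The Synopsis makes the same commitment without naming the parameters and without the qualifier: "For each subject, standard PK parameters will be calculated, based on the plasma concentrations of ATI-50002". Blood is drawn from the first six enrolled subjects on two occasions in the double-blind period, before application and 1, 2, 4, 8 and 24 hours after it (Protocol 9.3.2).

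The SAP deals with plasma in one sentence in 4.2.1: "The blood levels of ATI-5002 will be listed only" (compound number as printed). SAP 4.5, the section for pharmacokinetic analyses, covers scalp biopsy levels alone. SAP 4.1.1 defines a blood PK population (PK1), but apart from the head count in 4.1.2 no analysis is assigned to it. SAP 4.6 reports that an interim assessment of blood and scalp PK was carried out in the first six patients; it names no parameter and gives no result.

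SAP 4.8 records departures from the planned analysis. It drops the chi-square comparison of adverse events, sends the ALADIN and blood T-cell analyses to a separate document, and drops histology because there were few samples. Plasma parameters do not appear in it.

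**The concern.** A listing is not the analysis that the protocol planned. The parameters were fixed in the protocol: section 12.2 leaves only the PK and PD populations to be defined in the SAP. The word *only* in SAP 4.2.1 rules out any derivation.

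Because 4.8 is silent, a reader cannot tell whether the parameters could not be estimated, for example because most levels were below quantification, or were simply left out. The two explanations mean different things for systemic exposure. Plasma is the only direct measure of that exposure in this study. It is taken in six subjects during the 28-day period, and the open-label schedule, which covers 52 weeks of treatment, contains no PK blood sampling.

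**Working it through.** There is no figure in the plan to reproduce: Protocol 12.1 and SAP 4.7 both say that no formal power calculation was made. The check compares the texts and then counts what could be derived.

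**1. Commitment against delivery**
- Protocol 12.4: five parameters per sampled subject. SAP 4.2.1 and 4.5: none.
- Synopsis: standard parameters per subject. SAP: none named anywhere.
- Declared in SAP 4.8: chi-square test, ALADIN and T-cell analyses, histology. Not declared: plasma parameters.

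**2. Informative profiles**
- Samples: 6 subjects × 2 profiles × 6 times (0, 1, 2, 4, 8, 24 h) = 72. Profiles: 6 × 2 = 12. Both counts include vehicle subjects, whose samples should yield no drug parameters.
- The documents do not give the number of active subjects among the six. Assume that the planned 8 active and 4 vehicle are achieved and that the order is random without blocking. Then P(k active) = C(8,k) × C(4,6−k) / C(12,6), with C(12,6) = 924:
  - k = 2: 28 × 1 / 924 = 0.030
  - k = 3: 56 × 4 / 924 = 0.242
  - k = 4: 70 × 6 / 924 = 0.455
  - k = 5: 56 × 4 / 924 = 0.242
  - k = 6: 28 × 1 / 924 = 0.030
- The mean is 6 × 8/12 = 4, the range is 2 to 6, and P(3 to 5) = 868/924 = 0.94. Blocking would usually pull the count towards 4; the documents give no block size.
- Informative profiles: 2 × 2 = 4 up to 6 × 2 = 12, about 4 × 2 = 8 expected. All of these are before any loss to values below quantification, a number that the documents also do not give.

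**3. What the schedule supports**
- Cmax, Tmax and AUC0-t can be obtained wherever levels are quantifiable.
- Half-life and AUC0-∞ need a terminal slope. Sampling times after the peak are 4 if Tmax is 1 h, 3 if 2 h, 2 if 4 h and 1 if 8 h. If three points after the peak are required (an assumed working rule), only profiles with Tmax at 1 or 2 h qualify.
- As an illustration, Protocol 3.1 gives a half-life of about 9.0 h after oral dosing of the pro-drug. If it applied here with log-linear decline, the level at 24 h would be 0.5^(16/9) = 0.29 of the level at 8 h, so a low 8 h value could be unquantifiable by 24 h.

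**4. The two profiles are not alike**
- Day 1 is a first application. The second profile follows about four weeks of twice-daily use, and Appendix 1 tells subjects to apply on the evening before. Its pre-dose level may therefore not be zero, and extrapolating its AUC to infinity would include drug from earlier applications. It cannot be read as a single-dose value.

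**5. Visit-day wording (side point)**
- Protocol 12.4 places the serial samples on "Baseline/Day 1 (Visit 2) and Day 29 (Visit 7) at predose (0 hr), and 1, 2, 4, 8 hours after study medication application".
- The Synopsis has "Day 1 (Visit 2) and Day 28 (Visit 6) at predose (0 hr), 1, 2, 4, 8", and footnote 12 of the Schedule of Assessments has "Blood for PK sampling will be obtained on Day 1 (Visit 2) and Day 28 (Visit 6), just prior to study medication application". Protocol 7.1 and 9.3.2 and SAP 2 agree with these.
- Protocol 12.4 also puts the 24-hour sample on Day 29, which fits only an application on Day 28, and its scalp paragraph refers to the in-office application on Day 28. Its Day 29 wording for the serial samples therefore reads as a slip in the visit day.
- Footnote 9 of the schedule, in both documents, has the last application on the morning of Day 28 and then speaks of a once-daily in-office application on Day 29.

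**The case against.** The best defence is that the Synopsis states the PK endpoint as concentrations in blood and skin, and a listing reports exactly that. The parameters are a derivation, and protocol 12.4 asks for them only where possible. The SAP is open about listing only, blood PK had already been assessed at the interim, and listing only may follow from what was found. SAP section 4 also refers to a data handling and programming specifications document that is not available here.

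Part of this stands. The concentrations are reported and the data are not lost: a reader could take observed Cmax and Tmax from the listing, and could compute AUC0-t if sampling times are listed. It would be wrong to infer that the plasma part of the primary objective goes unreported.

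The rest does not close the gap. The qualifier excuses a parameter that cannot be estimated, but the SAP does not say that any could not be, and it gives a rule for values below quantification for scalp samples only. SAP 4.6 does not say that the interim assessment replaces the planned analysis. The specifications document is cited for general details, data handling and dates, not for PK parameters, and it could hardly reverse an instruction to list only.

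Three stronger readings should be resisted:
- *The parameters were dropped because of the unblinded interim results.* The documents give no reason at all, so they support neither this nor an innocent explanation.
- *All 72 samples and 12 profiles lose their analysis.* Those counts include vehicle subjects.
- *The Day 29 wording puts half of the profiles, 6 of 12, at risk.* Every section that governs sampling says Day 28, as does SAP 2, and protocol 12.4 is consistent with that through its own 24-hour sample. No profile is shown to be at risk.

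**Conclusion.** The point holds. The SAP does not deliver an analysis that the protocol planned under its primary objective, and the section meant for such changes does not record it. The gap is the derivation of five parameters and the reason for omitting them; the concentrations themselves are reported.

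In size, it concerns 4 to 12 informative profiles, about 8 expected, from 2 to 6 active subjects. This assumes that the planned 8:4 split is achieved; the expected value also assumes random order. The firm part is Cmax, Tmax and AUC0-t where levels are quantifiable. Half-life and AUC0-∞ may often not be estimable from this schedule. The study is small and descriptive, so this does not threaten a formal conclusion. It should still be put right, because it is cheap and these are the study's only plasma data. The visit-day wording is a minor inconsistency on which the main point does not depend.

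**What to change.** 1. In SAP 4.2.1 and 4.5, for the PK1 population, derive and list per subject Cmax, Tmax and AUC0-t where levels are quantifiable, and half-life and AUC0-∞ only where a terminal phase can be estimated, with the rule for that stated.
2. Treat Day 1 and Day 28 separately, and do not present an extrapolated AUC from the second profile as a single-dose value.
3. If plasma levels are mostly below quantification, report the number quantifiable and the maximum concentration instead, in keeping with the count already planned for scalp in SAP 4.5.
4. In SAP 4.8, record every parameter from protocol 12.4 that is not derived, with the reason. If the interim assessment is the reason, say so.
5. As a side correction, reconcile the Day 29 wording in protocol 12.4 and in footnote 9 of the schedule (both documents) with the Day 28 wording elsewhere.

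The cost is a small amount of programming, a few sentences in SAP 4.2.1, 4.5 and 4.8, and the wording corrections in item 5. No new samples or visits are needed.

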### **4.2.2 Scalp Biopsy Levels of ATI-50002**

Scalp biopsy levels of ATI-50002 will summarized with descriptive statistics for each schedule collection visit. Levels that are BLQ will not be included but will be accounted for categorically.

## **4.3 Pharmacodynamic Endpoints**

The baseline scores for SALT and ALODEX will be the last non-missing value collected  $\leq$  the date of the first application of double-blind study medication. This baseline will be used also for calculating changes during open-label for these variables. For the eyebrow assessments (CEA and SEA), the value collected at V7 will be used as the baseline for calculating changes during subsequent visits.

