9.4. Eyebrow Assessments (Open-Label Extension)

Subjects with eyebrow loss in one or both eyebrows will be allowed to treat their affected eyebrow(s) during the open-label period of the study. Both the investigator and subject will assess eyebrow loss at entry into the open-label extension and then monthly for the first 6 months, then at 9 and 12 months during the open-label treatment period. The Investigator will document the affected areas of the eyebrow or brow(s) on the source document and eCRF.

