9.4.1. Clinician's Eyebrow Assessment (CEA) (Open-Label Period)

The CEA is the Investigator's assessment of the affected eyebrow(s) at a particular point in time. The Investigator should NOT refer to any other assessments to assist with these assessments.

At Visits 8 - 16, the Investigator will assess the affected eyebrow(s) using the scale below and report the one integer that best describes the amount of eyebrow hair present. **If both eyebrows are affected, each eyebrow will be assessed separately.**

Clinician's Eyebrow Assessment

Grade	Descriptor
0	No eyebrow hair: No terminal hairs are visible in the affected area(s)
1	A little eyebrow hair: Occasional terminal hairs are visible in the affected area(s)
2	Some eyebrow hair: Numerous terminal hairs are visible in the affected area(s)
3	Most eyebrow hair: Mostly complete eyebrow regrowth with terminal hair in the affected area(s)
4	Full eyebrow hair: Complete eyebrow regrowth with terminal hair in the affected area (s)

9.4.2. Subject's Eyebrow Assessment (SEA) (Open-Label Period):

The SEA is the subject's assessment of the appearance of eyebrow hair present on the affected eyebrow(s) at a particular point in time. The subject should NOT refer to any other assessments to assist with these assessments.

At Visits 8-16, the subject will assess the affected eyebrow(s) using the scale below and report the one integer that best describes the amount of eyebrow hair present. **If both eyebrows are affected, each eyebrow will be assessed separately.**

Subject's Eyebrow Assessment

Grade	Descriptor
0	No eyebrow hair: No thick, coarse hairs are visible in the affected area(s)
1	A little eyebrow hair: A few thick, coarse hairs are visible in the affected area(s)
2	Some eyebrow hair: Numerous thick, coarse hairs are visible in the affected area(s)
3	Most eyebrow hair: The majority of the affected area(s) of the eyebrow is covered in thick, coarse hairs
4	Full eyebrow hair: The affected area(s) of the eyebrow is fully covered in thick, coarse hairs

An investigational staff member will identify the eyebrow to be evaluated by the subject, educate the subject on the SEA scale before each evaluation and direct the subject to assess the eyebrow, one eyebrow at a time. The staff member should not influence the subject's assessment.

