12.5.4. Secondary Analyses

Summary descriptive statistics (N, mean, median, SD) by visit will be provided for all efficacy parameters. Secondary efficacy parameters are described below:

The secondary efficacy endpoints include mean change from baseline in the SALT score at Week 28 (Visit 13), Week 40 (Visit 14) and Week 52 (Visit 15).

The percentage hair growth will be calculated as the mean change from Baseline (Visit 2) scores compared to end of treatment Week 28 (Visit 13), Week 40 (Visit 14) and Week 52 (Visit 15).

Mean change from baseline in the ALODEX score, proportion of subjects achieving a $\geq 50\%$ hair growth compared with baseline.

Treatment satisfaction will be summarized.

The ALODEX score analysis will use the same methodology as specified for SALT score analysis. Other parameters will be analyzed as detailed in the statistical analysis plan.

Mean change from baseline in eyebrow growth will be calculated as the mean change in the Clinician’s Eyebrow Assessment (CEA) from entry into the long-term, open-label extension compared to Week 28(Visit 13), Week 40 (Visit 14) and Week 52 (Visit 15). The CEA evaluates eyebrows on a scale from “No eyebrow hair” (Grade 0) to “Full eyebrow hair” (Grade 4).

Mean change from baseline in the Subject's Eyebrow Assessment (SEA) will be calculated from entry into the long-term open label extension to Week 28 (Visit 13), Week 40 (Visit 14) and Week 52 (Visit 15). The SEA evaluates eyebrows on a scale from "No eyebrow hair" (Grade 0) to "Full eyebrow hair" (Grade 4).

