 On Day 29 (Visit 7) subject may be given the option to move into open-label extension treatment. 
 
• If the subject declines the open-label extension, she/he should be seen for the Visit 16 (Post-treatment) assessments 30 days following the date of Day 29 (Visit 7).
 
• If the subject chooses to continue in to the open-label extension, she/he must sign an ICF prior to being dispensed open-label drug and receiving continued study medication application instructions.
 
• If the subject enrolls in open-label treatment after Day 29 (Visit 7), an unscheduled visit will be conducted in order to obtain consent, review drug application instructions, and dispense drug. This will be considered the official date that the subject initiated open-label extension treatment and the scheduling of subsequent visits 8-16 should be based off of this date as referenced by (OLE xxx) in the treatment day schedule header above.
 
											
 Subjects who are eligible and consent to enter the open-label extension will have a baseline CEA and SEA completed at Visit 7 or the unscheduled Visit.											

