## 4. STATISTICAL METHODS

In general summaries will be presented according to double-blind treatment group and additionally for the subset of patients entering open-label. Other than baseline data (ie data collected prior to the first application of double-blind medication), the data summarized corresponds to the period of collection (ie during double-blind or during open-label). For those entering open-label, the open label period begins at the application of open-label medication. Additional details are provided in the data handling and programming specifications document. No imputation of missing data was performed other than completely or partially missing dates as described in the Data Handling and Programming Specifications document.

All Data listings are sorted by double-blind treatment group and patient ID.

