### **4.3.2 Eyebrow Assessments during Open-Label**

For patients entering open-label, mean Percent hair loss, CEA and SEA scores mean and mean change from baseline will be provided by visit. At entry into open-label, V7, summary statistics will be provided by double-blind treatment group as well as for all patients entering open-label. Where applicable, each patient's scores for the left and right eyebrows will be averaged prior to summarization. Individual scores for the left and right eyebrows will be provided in the data listings.

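### The SAP takes the eyebrow (CEA/SEA) baseline only from Visit 7, although late entrants to the open-label extension have theirs scheduled at an unscheduled entry visit

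*SAP*

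**What the plan says.** SAP 4.3 gives one source for the eyebrow baseline: "For the eyebrow assessments (CEA and SEA), the value collected at V7 will be used as the baseline for calculating changes during subsequent visits". SAP 4.3.2 carries the same assumption into the entry summary: "At entry into open-label, V7, summary statistics will be provided by double-blind treatment group as well as for all patients entering open-label".

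The Schedule of Assessments, printed in both documents, is broader. Footnote 18 says that subjects who are eligible for and consent to the extension "will have a baseline CEA and SEA completed at Visit 7 or the unscheduled Visit". Footnote 17 explains the second option: "If the subject enrolls in open-label treatment after Day 29 (Visit 7), an unscheduled visit will be conducted in order to obtain consent". It makes that visit the official start of the OLE for the subject and counts Visits 8 to 16 from it.

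Elsewhere the reference point is OLE entry. Protocol 9.4 says that investigator and subject "will assess eyebrow loss at entry into the open-label extension and then monthly for the first 6 months". Protocol 12.5.4 defines CEA change from OLE entry and says that SEA change "will be calculated from entry into the long-term open label extension to Week 28 (Visit 13") and to the two later time points. The synopsis does the same. SAP Section 4 itself states: "For those entering open-label, the open label period begins at the application of open-label medication".

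**The concern.** Visit 7 and OLE entry are the same occasion only for subjects who roll over without a gap. The protocol recognises others. Administrative Letter #5 dealt with subjects who had an administrative delay between Visit 7 and OLE entry, and the synopsis and protocol 7.5 describe them in the past tense. For these subjects the SAP looks for the baseline at a visit where it need not have been collected, and ignores the visit where the schedule puts it.

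At stake is the eyebrow part of a stated secondary objective, in a study of about 12 subjects. On the literal rule the mean-change tables could rest on fewer subjects than the by-visit means beside them. The affected subjects would also be missing from an entry summary that is meant to cover everyone entering the OLE.

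**Working it through.** **Do Visit 7 and OLE entry coincide?** The schedule gives each open-label column a study day and an OLE day. Study day minus OLE day:

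57-28, 85-56, 113-84, 141-112, 169-140, 196-167, 197-168, 211-182, 281-252, 365-336 and 393-364 all equal 29.

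So Day 29 (Visit 7) is OLE day 0 only when there is no gap. For a late entrant, footnote 17 makes the unscheduled visit OLE day 0.

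**Where is a late entrant's baseline?** Footnote 18 ties the baseline CEA/SEA to subjects who are eligible and consent. Footnote 17 places a late entrant's consent at the unscheduled visit. Read together, the baseline would normally be collected there. The version history dates the Day 29 eyebrow assessment to Version 2.0, so anyone who had passed Visit 7 before then had no scheduled Visit 7 score. Such subjects are part of the late-entry group, not an additional one.

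**What happens under the literal rule?** SAP Section 4 imputes dates only, so a missing Visit 7 score stays missing and no change can be calculated.

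**Loss per affected subject** (left and right eyebrows averaged, as in SAP 4.3.2, and all visits attended):

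- Scheduled post-entry CEA/SEA visits: 8 to 16, which is 9 (schedule; protocol 9.4.1 and 9.4.2).
- Change values: 9 visits x 2 scales = 18.
- At the protocol-named Weeks 28, 40 and 52: 3 x 2 = 6.
- If all 12 subjects entered the OLE with eyebrow loss, the full sets are 12 x 18 = 216 and 12 x 6 = 72. The share per affected subject is 18/216 = 6/72 = 1/12 = 8.3%.
- With 8 or 6 such entrants (assumed), the share is 1/8 = 12.5% or 1/6 = 16.7%.

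**Number of subjects with a computable change.** Let m be the OLE entrants with eyebrow loss and k those whose only baseline is at the unscheduled visit. The documents give neither. The literal rule allows at most m - k; a baseline anchored to OLE entry allows m. For an assumed m = 12:

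| k | Literal Visit 7 rule | Entry-anchored rule |
|---|---|---|
| 0 | 12 | 12 |
| 3 | 9 | 12 |
| 6 | 6 | 12 |
| 12 | 0 | 12 |

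**If a late entrant does have a Visit 7 score,** a change can be calculated, but it spans the gap before open-label treatment and is not the change from OLE entry that protocol 12.5.4 defines.

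**The case against.** The strongest defence is that Visit 7 is shorthand for the OLE-entry record. SAP 4.3.2 promises a summary of everyone entering the extension, which the literal reading would break, and footnote 18 in the same SAP names both visits. The separate Data Handling and Programming Specifications, which are not available here, could map the unscheduled visit to Visit 7. In that case the tables would be right and SAP 4.8 would have no change to report. This is possible. But footnote 18 offers the two visits as alternatives, which does not fit their being synonyms, and SAP 4.3 states an explicit rule without deferring to another document. If a mapping exists, the SAP should say so.

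Other points limit the consequence, and they stand:

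- The documents do not say how many late entrants there were or how many lacked a Visit 7 score. That their baseline falls at the unscheduled visit is an inference from consent timing, though a reasonable one.
- The count of 18 assumes full attendance and includes post-treatment Visit 16. Protocol 9.4 alone lists monthly assessments to 6 months and then months 9 and 12, which is 8 occasions. The 6 values at the named weeks matter most.
- Eyebrows are not treated before the OLE, and protocol 3.1 calls spontaneous regrowth in these patients rare, so an existing Visit 7 score should be close to the entry score.
- The analysis is descriptive and uncontrolled, with no test or error rate involved. By-visit means are unaffected, and the listings show individual scores.

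**Conclusion.** The concern holds. As written, the SAP's baseline rule conflicts with its own schedule and with the protocol's definition of eyebrow change, and SAP 4.8 does not record the difference. Each late entrant without a Visit 7 score loses all 18 scheduled changes, 6 of them at the named weeks. That is at least 8.3% of the maximum data set, given that no more than 12 subjects entered with eyebrow loss. The total loss lies between none and all of the change data, because the counts are not stated.

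The conclusion rests on a literal reading of the SAP and would lose its practical effect if the programming specifications re-map the visit. The rule is correct for subjects with no gap. This should be fixed, but it does not threaten the study's primary objective.

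**What to change.** In SAP 4.3, replace the eyebrow sentence with: *For CEA and SEA, baseline is the last non-missing value collected on or before the date of the first application of open-label study medication (Visit 7 or the unscheduled OLE-entry visit).* In SAP 4.3.2, change the reference to Visit 7 as the point of entry to: *At OLE entry (Visit 7 or the unscheduled visit).*

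This follows the date-anchored form that SAP 4.3 already uses for SALT and ALODEX, with the first open-label application as the anchor. Results for subjects with no gap do not change. The cost is two phrases and a small programming change; the entry assessment is already scheduled, so no further data collection is needed. If the programming specifications already map the visit this way, the edit only brings the SAP text into line.
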